14. ANALYSIS PLAN

General. After the data have been cleaned, we will examine the distribution and dispersion of data through descriptive numerical summaries and graphical tools such as scatter plots and box plots, probability plots, scatter matrix plots, co-plots, and trellis graphics to assess distributional assumptions and relationships among important variables. Before attempting a longitudinal analysis of the change in our outcomes using a linear mixed model, we will use profile plots, empirical summary plots and correlograms to guide us in the formulation of our model.¹⁸⁵ Some data will be subjected to scale transformation (e.g., logarithmic), as needed, to meet statistical assumptions. Box Cox or Yeo-Johnson transformations may also be used for this purpose.

Because missingness can potentially spoil or invalidate a study, we will spare no effort to minimize incomplete or missing data. All data will be carefully inspected to identify missing items, outliers, or other influential features. We will strive to form conclusions that are robust to different missing-data mechanisms,¹⁸⁶ and we will consult with colleagues in the Fielding School of Public Health Biostatistics Department regarding the use of incomplete-data analysis strategies that make effective use of available information.

Preliminary analyses will compare treatment groups on descriptive and clinical characteristics at baseline to ensure that randomization has succeeded. SAS (PC version 9.3) and Stata (Intercooled version 13) comprehensive database management and statistical packages will be used for descriptive calculations, group comparisons, and conditional regression modeling.

Experimental contrasts will be examined *a priori* using Stata's mixed effects modeling procedures, with standard errors corrected for the effects of clustered data.¹⁸⁷ It is known that even with randomized designs, covariate imbalance between treatment groups can exist and threaten the integrity of the design.¹⁸⁸ Because the potential bias may result in misleading conclusions, we will perform a thorough examination for covariate imbalance. Specifically, we will examine the distributions of all important variables at baseline and at the major endpoint (12 months follow-up), and also at intermediate points if the covariate is time-varying. Formal statistical methods for testing selection bias (systematic baseline imbalances) based on response data will be followed.^{188,189}

Missing and incomplete data

Prevention is far superior to a statistical cure, and every effort will be made to collect outcome data on all randomized participants. For example, we will ask medical staff at the clinical practices to obtain weight measurements on individuals who have stopped participating in the trial. Due to the high longitudinal correlation, missed "interior" visits won't decrease information very much for a linear trend. However, they are needed to assess departures from a linear trend. As detailed in Little and Rubin 2002¹⁹⁰ and discussed by Mealli,¹⁹¹ the underlying missing data process determines the biasing effects of missing data and structures valid analytic strategies. If data are missing completely at random, then there is no induced bias and a complete case analysis, while inefficient, is valid. Another approach to dealing with missing 12-months follow-up weights is to conduct "liberal" and "conservative" analyses. One would assume that on average there is neither weight loss nor gain, $[W_{12} - W_0 = 0]$.

Censoring

In certain analyses, data may be censored. Types of potential censoring include:

Patterned after protocol published online in association with Appel et al. (2011)¹⁵

1. Medical event censoring – a medical event (e.g. stroke, heart attack, or pregnancy), use of certain medications, or death. In this case, a weight may or may not be available. If available, the weight may be strongly influenced by the condition (e.g. extreme weight gain from use of oral steroids) such that the weight data should not be used subsequent to the event.
2. Dropouts not associated with a particular event (e.g., a participant refuses to continue). For our primary analysis we will use the weight change data for the pre-dropout period. Sensitivity analyses will evaluate the consequences of imputing subsequent weights using a statistical model, last-observation-carried-forward (equivalent to imputing 0 weight change subsequent to the dropout), or imputing a non-zero monthly weight gain subsequent to dropout.

Intent to Treat Analyses

Primary analyses will be performed on an intention-to-treat (ITT) basis. However, interpretation of weight loss trials is complicated because of drop-out from the intervention group and drop-in from the control group. Particularly common are early drop-outs, i.e. individuals randomized to intervention who attend only a few intervention sessions, sometimes none. Such persons are included in ITT analyses. In this setting, we will compute “on treatment” comparisons and variations on this approach that adjust such an analysis for differential correlates of adherence in the treatment groups.

Care is needed in answering such questions, and Bellamy et al, Mealli et al. ^{191,192} provide a useful framework for such analyses. For a basic case, we consider how to handle participants who complete at most 2 intervention sessions. They will be included in the primary, as randomized, intent to treat analysis. A secondary question is, “how does the treatment groups compare for those who adhered to treatment?” A straightforward comparison of treatments based only on “compliers” is attractive, but is biased if the compliers differ among the treatment groups. A valid comparison depends on adjusting for these differences, being careful not to adjust away the treatment effect. Propensity score approaches using information available at randomization and up through the first session can adjust for this imbalance. More sophisticated approaches using time-varying propensities allow accommodating more complicated patterns of non-adherence.

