Randomization procedure. If all screening and baseline measures indicate that the patient remains eligible, a programmed application in REDCap generates a random assignment to experimental condition for the patient at the end of the screening assessment. The lifestyle change coaches can look up in REDCap's database the study participants assigned to their condition. The coach will then call the patient and arrange for the first coaching session, if appropriate. The research assistants will be kept ignorant of the patient's assignment to experimental condition, to reduce the chance for bias. Of necessity, the lifestyle change coaches will be aware of the patient's experimental assignment but will be instructed to follow the protocol carefully, so as not to introduce any personal bias.

The REDCap data entry system has also been programmed to generate a randomly determined assignment to condition, if the would-be participant met all inclusion criteria and reported no exclusion criteria. Hence, at the completion of the screening visit the study participant will be informed about the experimental condition that he/she had been assigned to and the name and contact number of his/her lifestyle coach. More information about the randomization process is provided below.

Follow-Up (FU) Visits: Participants will be asked to attend in-person follow-up visits at 6 and 12 months after randomization. Most of these data will be collected in-person at the clinic but the FFQ may be administered over the phone, depending on the time constraints of the study participant. The target windows used to schedule participants will coincide with a one month period around the 6 and 12 months follow-up visits. During follow-ups, we will also ask patients to evaluate the trial, including their perceptions of the acceptability and usefulness of the intervention and its components (MyPlate or Calorie Counting).

Measurement intervals.

Most measures will be assessed at baseline, at 6 months and 12 months follow-up. The Block Food Frequency Questionnaires will be administered only at baseline and 12-months follow-up, not at 6-months follow-up, to minimize the burden on study participants. Questionnaires were administered in the order described below in Table 4.

Table 4: Data Collection Items and Schedule by Contact

	Screening	Baseline	F-up-6	F-up-12
Eligibility/Interest	X			
Informed Consent	X	X		
Weight (self-reported)	X			
Height (self-reported)	X			
Weight (measured)		X	X	X

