Primary Patient Medical Outcome: Weight (kg) will be measured at each assessment in the clinic setting. Weight in light indoor clothes without shoes will be recorded by trained, certified staff using a high-quality digital scale (Tanita). Duplicate measurements will be made to ensure accuracy. Weight will be measured in pounds for ease of interpretation by the participants and subsequently converted to kilograms for data analysis. Scales will be calibrated weekly using standardized weights. The weight at screening/baseline will be used to determine eligibility ($27.0 \leq \text{BMI} \leq 40.4$). The difference between body weight obtained at screening/baseline and 12 months follow-up will be the primary patient medical outcome.

Secondary patient-centered outcomes include: weight control self-efficacy, patient autonomy, health-related quality of life, and patient satisfaction.

Weight control self-efficacy will be assessed using the 8-item short version ¹²⁷ of the 20-item Weight Efficacy Life-style Questionnaire (WEL), a measure judged reliable and valid in obese populations.^{128,129} The WEL-SF provides a total weight self-efficacy score based on the sum of the item scores (total range = 0– 80). Higher scores indicate greater self-efficacy. The WEL has demonstrated good internal consistency reliability in a general overweight patient population (Cronbach's coefficient alpha = 0.95 for men, 0.93 for women).^{129,130} The WEL-SF correlates $r = .968$ (shared variance = .937) with the WEL, despite the 60% reduction in the number of items.¹²⁷ Because of the high shared variance, the short version was chosen over the long version in order to minimize respondent burden.

Patterned after protocol published online in association with Appel et al. (2011)¹⁵

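### Read literally, the dropout rule in Section 14 leaves clinic weights retrieved after dropout out of the primary 12-month weight analysis

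*Combined protocol and SAP*

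**What the plan says.** Five statements bear on this point, all in the combined protocol and SAP.

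- **Section 14, Missing and incomplete data.** The aim is that "every effort will be made to collect outcome data on all randomized participants". The example given is that "we will ask medical staff at the clinical practices to obtain weight measurements on individuals who have stopped participating in the trial".
- **Section 14, Censoring, item 2** (dropouts not tied to a particular event): "For our primary analysis we will use the weight change data for the pre-dropout period". Sensitivity analyses then impute the later weights by a statistical model, by carrying the last observation forward, or by adding a monthly gain. No use of an observed post-dropout weight is named.
- **Section 14, Intent to Treat Analyses:** "Primary analyses will be performed on an intention-to-treat (ITT) basis". Of people who leave the intervention early it says: "Such persons are included in ITT analyses".
- **Section 8, Primary Patient Medical Outcome:** "The difference between body weight obtained at screening/baseline and 12 months follow-up will be the primary patient medical outcome".
- **Section 8, Follow-Up Visits:** "Participants will be asked to attend in-person follow-up visits at 6 and 12 months after randomization".

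Censoring item 1 is a separate rule for medical events and certain medications. It says that weights strongly influenced by the event should not be used afterwards.

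**The concern.** The plan sets out to collect a weight after dropout and then gives that weight no place in the primary analysis. Two analysts working from this text could build different primary datasets, one with the retrieved weights and one without.

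Study weights are scheduled only at 6 and 12 months. Someone who leaves before 6 months has no post-baseline study weight, and someone who leaves later has at most a 6-month change. For these people a retrieved clinic weight may be the only direct observation of the 12-month endpoint. A mixed model fitted to pre-dropout data would fill the gap under a missing-at-random assumption. It would then estimate what would have been seen had people continued, rather than the 12-month difference among everyone randomized.

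The hypothesis that both arms show significant and similar 12-month declines in weight depends on the within-arm change, so regain after dropout matters even when the arms behave alike. The between-arm contrast is exposed only when they do not. The sponsor's own rationale (Section 3, Part B) attributes much of the relapse in weight-loss trials to the deprivation that comes with calorie counting, so unequal regain is a live possibility here. The hunger outcome is not touched by this rule.

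**Working it through.** The point concerns which data enter the analysis. The plan states no figure for it that could be reproduced, so the arithmetic below only illustrates scale.

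**Reading the text**

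1. Item 2 appears in a list of types of censoring, names the primary analysis, and makes no exception for a weight that is available.
2. Item 1 considers both the case where a later weight exists and the case where it does not, so the authors had observed post-event weights in mind.
3. The subsection opens by saying that data may be censored in certain analyses. That hedge does not override a sentence that specifies the primary analysis.
4. No other section says that retrieved weights enter the primary model. The General part of Section 14 promises consultation on incomplete-data strategies, which does not settle the matter.

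**Inputs from the plan**

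- Sample size 261 (Section 4, reduced from 300).
- Attrition 20% (Section 13, stated for 6 months; no 12-month figure is given).
- Planning differences in weight loss (Section 13): 7.9 − 6.4 = 1.5 kg and 5.4 − 3.4 = 2.0 kg.

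**Assumptions not in the plan**

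- Dropouts' true 12-month weight lies 1 to 3 kg above what the pre-dropout data imply (called regain below).
- Where the arms differ, dropout is 15% in one and 25% in the other.
- Clinics retrieve a 12-month weight for half of the dropouts.
- The 20% applies at 12 months, and all of it is non-event dropout.

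**People affected**

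- 0.20 × 261 = 52.2, about 52, leaving about 209 with a 12-month study weight.
- Retrieving half of the 52 adds 26: 209 + 26 = 235, and 26 / 209 = 12% more.

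**Overstatement of mean loss within an arm** = dropout share × regain

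- 0.20 × 1 kg = 0.2 kg; 0.20 × 3 kg = 0.6 kg.

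**Bias in the arm difference** = difference between arms in (dropout share × regain)

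- Equal dropout and equal regain: 0.
- 15% versus 25% dropout, equal regain: (0.25 − 0.15) × 1 kg = 0.1 kg; (0.25 − 0.15) × 3 kg = 0.3 kg.
- 20% dropout in both arms, regain of 1 kg versus 3 kg: 0.20 × (3 − 1) = 0.4 kg.

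**What the rewording recovers** = retrieval rate × bias, if the retrieved people are representative and the rest are handled as before

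- Within an arm, at half retrieved: 0.5 × 0.2 = 0.1 kg to 0.5 × 0.6 = 0.3 kg.
- Arm difference at 15% versus 25%, half retrieved: 0.5 × 0.1 = 0.05 kg to 0.5 × 0.3 = 0.15 kg.

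**The case against.** The strongest reply is that item 2 means only this: where no later weight exists, analyse what was observed and impute nothing. One imputes only what was not observed, and item 2, unlike item 1, does not say that an available weight must be set aside. That reading fits the planned mixed model and the stated collection aim. It may be what the authors intended, but the sentence does not say so, and the plan should not leave the reader to guess which weights form the primary dataset.

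A second reply is that regain after dropout is already probed. The plan includes an imputed monthly gain, last observation carried forward, and an analysis assuming no net weight change at 12 months for missing weights. This stands as mitigation. It does not explain why a weight the trial hopes to measure should be represented by an assumed one.

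A third reply concerns quality. Study weights are duplicate readings by certified staff on scales calibrated weekly, and follow-up collectors are masked. None of this is promised for clinic weights, and some people who refuse to continue may not have agreed to later use of their records. This stands, and the remedy has to allow for it.

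A reader might go further and infer that the trial is throwing away outcomes already in hand, or that it abandons intention-to-treat. The documents support neither. The weights are planned, with no timing or yield stated. Dropouts stay in their randomized arm, and those with few sessions are expressly kept in the primary analysis. The tension concerns the use of outcome data, not the exclusion of people.

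**Conclusion.** The concern holds as a defect in the wording of the primary weight analysis. As written, item 2 omits retrieved 12-month weights after non-event dropout, which does not match the endpoint or the intention-to-treat use of outcome data.

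The likely size is modest. Within-arm loss is overstated by 0.2 to 0.6 kg under the stated assumptions. The arm difference is unaffected if dropout and regain are equal, and is biased by 0.1 to 0.3 kg at 15% versus 25% dropout, against planning differences of 1.5 to 2.0 kg. These figures are the whole assumed bias; the rewording removes only the part that retrieval reaches. Regain, the dropout split and the retrieval rate are all assumptions, and the 20% is a 6-month figure. The change is worth making because collection is already planned and the remedy is mainly wording; the point does not threaten the trial.

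**What to change.** Reword Censoring item 2 along these lines:

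- The primary intention-to-treat weight model uses all observed 6- and 12-month weights. This includes clinic weights retrieved after non-event dropout, provided they fall within a stated window around the visit and consent permits their use. The one-month scheduling window in Section 8 is a natural candidate.
- Each weight carries an indicator of its source (study scale or clinic).
- The missing-data model is relied on only where no weight exists.
- The pre-dropout-only analysis becomes a sensitivity analysis, alongside the imputation analyses already listed.
- A further sensitivity analysis is restricted to study-scale weights.

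This edit leaves the item 1 medical-event rule as it stands.

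The cost is a few sentences in the SAP, one extra data field and one extra sensitivity analysis. The downside is measurement quality, since clinic weights are not promised the calibration, duplicate readings or masking of study weights. The source indicator and the study-scale analysis make that visible but do not remove it.

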15. DATA MANAGEMENT

Data will be collected from three main sources: 1) data entered by participants on Dell tablet PCs; 2) data entered by lifestyle change coaches during coaching sessions; 3) REDCap data entry by trial fieldwork staff of selected data (e.g. randomization date, clinic ID, recruitment data, clinical measurements, and attendance). Data entry is accessible via the secured websites. Web based data entry systems will include range and cross checks. All hard copy data forms will undergo editing/checking by a second Research Assistant. Missing and questionable data will be followed-up and corrected. Data clerks will perform data entry as soon as possible after receipt of forms. All data entered will pass through an extensive computer editing system with imbedded checks for internal consistency and biologic plausibility. All data centrally entered will be 100% verified. Daily back-ups of all study data will be done in the secured server and stored off-line on tape and/or laserdiscs in a locked area.

Data confidentiality

The investigative team is keenly aware of the need to protect participant confidentiality, as well as corresponding legal requirements, including those mandated by HIPAA (Health Insurance Portability and Accountability Act). All data collected and stored electronically will be password

protected and saved in a secured fashion. All study related computers will be under firewall protection and will maintain automated virus update mechanisms. Timely notification regarding relevant patches will be provided. Hard copy of the data collection forms will be stored in locked cabinets or areas. Only authorized personnel will have access to these locked areas. In addition, all study staff annually sign a confidentiality statement attesting to their understanding of, and willingness to abide by, the staff written policies on research ethics and confidentiality. Access to the data entry website is password protected and restricted to personnel trained to use the system.

Data analysis

The data management team conducts all analysis of study data under the direction of the principal investigators and the trial statistician. A trial statistician will be assigned to all approved papers. Working with the lead investigator, the statistician will develop an appropriate analysis plan. Formal written analysis requests are reviewed for clarity before work is begun. This procedure minimizes rework and thus makes most efficient use of staff resources.

Analysis guide

To facilitate data analysis requests, the data management team will create a detailed analysis guide for the study investigators. This guide provides detailed, organized documentation of all study variables along with a process that allows researchers to request analyses in a clear, concise fashion. A summary data set including the most frequently used variables is provided, with variables in alphabetical order. Copies of every data form used in the study are also provided, each labeled with the specific variable name in the response field.

Trial-wide data release. The data management/analysis team will prepare and distribute a limited access dataset to the PCORI project office for public use with the analysis guide. The data release documentation provides detailed, organized documentation of study variables and clear instructions on how to install and access the data.

16. TRIAL ADMINISTRATION – Organization of investigators and project staff

The UCLA/TCC study operation will be organized into teams of investigators and staff. The type and number of subcommittees, ad hoc working groups, and other units depends on the phase of the trial and study needs. The organizational structure will be reviewed periodically and amended accordingly. Hence, the organizational structure summarized below, which is appropriate for the early implement phase of the trial, will likely change over time. The primary decision-making body is the Oversight Committee, chaired by the PIs and comprised of all investigators and senior staff (e.g., Intervention Director). This committee, which convenes monthly, reviews the progress of all components and focuses on high level scientific and administrative issues. This committee will also guide publications. An administrative subcommittee, comprised of the UCLA PI ([name]) and Co-PI ([name]) from UCLA, the PI from TCC ([name]), and a few senior staff, meets weekly and addresses day-to-day operational issues and sets short-term priorities. The following are other working units of the trial:

- Field Operations Subcommittee, which focuses on recruitment, retention, measurements, quality assurance, quality control, and data collection.
- Intervention Subcommittee, which focuses on the design and implementation of the interventions.
- Data Management and Analysis Subcommittee.

